4.6.2 Subject Disposition

The number of subjects included in each analysis population (PP and Safety) will be summarized, as well as the reasons for exclusion from the population. The number of subjects completed and discontinued (including the reasons for discontinuation) will be summarized.

4.6.3 Demographic and Baseline Characteristics

Subject demographic and baseline characteristics will be summarized descriptively for the PP and safety populations. Demographic and baseline variables will include variables such as age, height, weight and BMI. OB-GYN history variables will also be summarized. Demographic and baseline variables as well as OB-GYN history variables will be summarized using descriptive statistics.

4.6.4 Efficacy Analyses

Efficacy evaluations will be summarized descriptively, by visit.

4.6.4.1 Primary Efficacy Analysis

Final Outcome will be presented using frequency counts and percentages for No New Adhesions at Week 6 and Adhesions at Week 6. Specifically, Final Outcome will be determined based on agreement in hysteroscopy evaluation between 2 out of the 3 Independent Readers. The ESH score will also be summarized using descriptive statistics for baseline (both Investigator and Independent Reader) and the Week 6 visit (Independent Reader only). The Final Outcome assessment will be done for both the Safety and Per Protocol populations. In either population:

- For subjects whose final 6-week hysteroscopy determination per agreement by two out of three Independent Readers shows Adhesion(s):
 - o Final Outcome is **New Adhesion** if the final baseline hysteroscopy determination per agreement by two out of three Independent Readers showed No Adhesion.
 - o Final Outcome is **Undetermined** if the final baseline hysteroscopy determination per agreement by two out of three Independent Readers showed Adhesion.
 - o Final Outcome is **Undetermined** if there were no evaluable hysteroscopy at baseline.
- For subjects whose final 6-week hysteroscopy determination per agreement by two out of three Independent Readers shows presence of No Adhesion(s):
 - Final Outcome is No New Adhesion.

In addition, a reader agreement analysis will be presented using frequency counts and percentages for the Baseline and the Week 6 visits.

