4.2.2 Exclusion Criteria

- 1) Preexisting adhesions within the endometrial cavity as indicated by an ESH score \geq I as determined by the investigator
- 2) One or more Type 0 fibroids and/or endometrial polyps of any size
- 3) Any reason for which, in the opinion of the Investigator, the individual study patient is not appropriate or suitable for participation in this study

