4.6 Statistical Methods

All statistical processing will be performed using SAS® unless otherwise stated.

Continuous variables will be summarized descriptively using number of subjects (n), mean, standard deviation (SD), minimum, median, and maximum. Categorical variables will be summarized descriptively using frequency counts and percentages.

Analyses presented for the Per-Protocol (PP) will be considered primary.

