4.6.1 Analysis Populations

The safety population will be comprised of subjects who received study treatment.

The Per-Protocol population (PP) will be comprised of subjects in the safety population who have a post baseline assessment, an evaluable hysteroscopy at Baseline and Week 6 follow-up and completed the Week 6 follow-up visit.

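### The primary incidence of new adhesions has no planned confidence interval, and its two table categories leave Undetermined women unplaced

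*SAP*

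**What the plan says.** **Summary measure.** Section 4.6 sets the general rule: "Categorical variables will be summarized descriptively using frequency counts and percentages". Section 4.6.4 adds "Efficacy evaluations will be summarized descriptively, by visit". Section 4.6.4.1 applies this to the primary variable: "Final Outcome will be presented using frequency counts and percentages for No New Adhesions at Week 6 and Adhesions at Week 6". No confidence interval or standard error is planned for it anywhere in the SAP.

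**Design.** The study has a single arm (4.1) and enrols at most 60 women. It is described as exploratory and unpowered (4.6.8).

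**Analysis sets.** Section 4.6 states "Analyses presented for the Per-Protocol (PP) will be considered primary". Section 4.6.1 requires for that set "an evaluable hysteroscopy at Baseline and Week 6 follow-up". Safety is every treated woman. Section 4.6.4.1 assigns the Final Outcome in both sets.

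**Classification rules (4.6.4.1).**

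- Adhesion at Week 6 and baseline clear per the readers: New Adhesion.
- Adhesion at Week 6 and baseline adhesion per the readers: Undetermined.
- Adhesion at Week 6 "if there were no evaluable hysteroscopy at baseline": Undetermined.
- No adhesion at Week 6, whatever the baseline: "Final Outcome is No New Adhesion".

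**Entry.** Section 4.2.2 excludes "Preexisting adhesions within the endometrial cavity as indicated by an ESH score" of I or more. The investigator makes that judgement, not the independent readers.

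**The concern.** There is no control arm and the SAP gives no reference rate, so the estimated incidence and its uncertainty are the whole of the primary result. The objective (section 3) is to record whether new adhesions occur, so a count at or near zero must be catered for. That is where a percentage alone says least: 0% of 60 women and 0% of 40 women print as the same percentage but support different statements.

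The percentage is also not fully specified. Two categories are displayed and three are generated. Every Undetermined woman has an adhesion at Week 6, so the second display label, read literally, covers her. The variable itself (4.5.1.1) concerns newly formed synechiae, which her data cannot establish. The SAP does not say whether she is an event, a member of the denominator only, or neither. In Safety it also does not say whether a treated woman with no Week 6 determination stays in the denominator; 4.6.9.2 says only that missing data are not imputed.

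Finally, some women who can never be classed as New Adhesion can still enter as No New Adhesion, which pulls the percentage down.

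**Working it through.** **Inputs.** From the SAP: n is at most 60 (4.6.8). The SAP gives no expected event rate, dropout rate or precision target, so there is no stated figure to reproduce. Event counts, smaller n and baseline splits below are assumptions.

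**Step 1: precision of the primary percentage.** For x events in n women, the exact (Clopper-Pearson) two-sided 95% limits are

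- lower = 2.5% quantile of Beta(x, n − x + 1), or 0 if x = 0;
- upper = 97.5% quantile of Beta(x + 1, n − x), which for x = 0 is 1 − 0.025^(1/n).

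For 0/60: 1 − 0.025^(1/60) = 1 − 0.9404 = 5.96%.

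| Events / n | Percentage | Exact 95% limits |
|---|---|---|
| 0/60 | 0% | 0 to 6.0% |
| 1/60 | 1.7% | 0.04 to 8.9% |
| 3/60 | 5.0% | 1.0 to 13.9% |
| 0/50 | 0% | 0 to 7.1% |
| 0/40 | 0% | 0 to 8.8% |
| 0/30 | 0% | 0 to 11.6% |

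Sixty is a ceiling, so for a zero count 6.0% is the best upper limit available. If the true incidence were 3%, the chance of seeing no event is 0.97^60 = 16% with 60 women and 0.97^40 = 30% with 40.

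**Step 2: who can be an event.** Among women with a Week 6 determination, let

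- a = women whose baseline the readers call clear;
- x = those among a who have an adhesion at Week 6 (New Adhesion);
- c = women with a reader-determined baseline adhesion or no evaluable baseline who are clear at Week 6 (No New Adhesion);
- u = women with the same baseline problem and an adhesion at Week 6 (Undetermined).

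Only the a women can become New Adhesion. The possible percentages are ordered

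x/(a + c + u) ≤ x/(a + c) ≤ x/a.

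Both denominators that include c are therefore low compared with women at risk. The shortfall factor is a/(a + c + u) if Undetermined women are kept, or a/(a + c) if they are dropped.

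**Step 3: illustration (all counts assumed).** Take a = 54, x = 1, c = 4, u = 2.

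| Reading | Result | Exact 95% limits |
|---|---|---|
| Undetermined in denominator only | 1/60 = 1.67% | 0.04 to 8.9% |
| Undetermined dropped | 1/58 = 1.72% | 0.04 to 9.2% |
| Women at risk only | 1/54 = 1.85% | 0.05 to 9.9% |
| Undetermined counted as events | 3/60 = 5.0% | 1.0 to 13.9% |

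The shortfall factors are 54/60 = 0.90 and 54/58 = 0.93. The first three rows differ by less than 0.2 percentage points.

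**Step 4: how c and u arise in each set.** Per-Protocol requires an evaluable baseline hysteroscopy, so there c and u need the readers to see a baseline adhesion that the investigator did not. In Safety, women with no evaluable baseline add to both. If c = u = 0, all four rows agree and only the missing interval remains.

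**The case against.** The plan is openly descriptive. It has no hypothesis, comparator or success threshold for an interval to decide. Counts are reported next to percentages, so a reader sees the zero as well as the 0% and can compute exact limits. This stands in part: nothing printed would be numerically wrong, and no test or power calculation is owed. But being exploratory explains the lack of a test, not the lack of a stated precision for a single estimated proportion.

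The classification asymmetry can also be defended: a woman clear at Week 6 has no new adhesion, whatever her baseline. As a label for her, that is correct. It does not make her suitable for the denominator of an incidence in which she could not have been counted as a case.

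A reader might infer several stronger points, which the SAP does not support:

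- *That the denominator is altogether open.* It is not. Sections 4.6 and 4.6.1 fix the sets and make Per-Protocol primary. What is open is the place of Undetermined women and, in Safety, of women without a Week 6 determination.
- *That the handling of Undetermined could triple the reported rate.* The move from 1.7% to 5.0% needs assumed counts and a literal reading of the second display label. The rules list New Adhesion and Undetermined as separate outcomes and the variable concerns newly formed synechiae, so a loose label is the likelier explanation.
- *That dropping Undetermined women lowers the rate.* Against keeping them in the denominator it raises it (1/58 against 1/60). It is low only against women at risk (1/54).

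**Conclusion.** The point holds as a reporting gap of minor to moderate weight. The SAP plans no precision for its main result. With a zero count the unstated exact 95% upper limit would be 6.0% at the maximum of 60 women and 8.8% at 40. The display categories do not match the rule categories, and Undetermined women have no stated place. A percentage over all classified women is somewhat low compared with women at risk, by a factor equal to the share of women with a reader-determined clear baseline. The SAP gives no figure for that share. In Per-Protocol the effect is probably small, because it depends on readers and investigator disagreeing at baseline; in Safety it may be larger. The limits in the first table rest only on binomial sampling and the n shown; the 54/4/2 split is purely illustrative.

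**What to change.** In section 4.6.4.1:

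1. Present the proportion of women with New Adhesion with an exact (Clopper-Pearson) two-sided 95% confidence interval, in Per-Protocol (primary) and in Safety.
2. Define the denominator as women with a final reader determination of No Adhesion at baseline and a final reader determination at Week 6.
3. Replace the second display label with the rule categories, so that the table shows New Adhesion, No New Adhesion and Undetermined.
4. Give separate rows for Undetermined women, for women with a baseline adhesion or no evaluable baseline (by Week 6 result), and for women without a Week 6 determination.
5. Optionally, add the interval over all women with a Week 6 determination with Undetermined counted as events. Label it a worst-case bound only, because it counts adhesions that the readers already saw at baseline, or that have no evaluable baseline, as if they were new.

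The cost is a few sentences in the SAP and a few output lines per set. The denominator may be slightly smaller and the upper bound will look less favourable than a bare percentage. No hypothesis test, larger sample or change in study conduct is needed.

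### The Final Outcome rule checks the readers' baseline only when Week 6 shows adhesions, and the two displayed categories leave Undetermined women and the denominator unsettled

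*SAP*

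**What the plan says.** SAP section 4.6.4.1 derives the Final Outcome from the majority of the independent readers.

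- **Week 6 shows adhesions.** The outcome is New Adhesion if the readers found none at baseline. It is Undetermined if they found an adhesion at baseline, or "if there were no evaluable hysteroscopy at baseline".
- **Week 6 shows none.** "Final Outcome is No New Adhesion", with no condition on baseline.

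The display is set in the section's opening sentence: "Final Outcome will be presented using frequency counts and percentages for No New Adhesions at Week 6 and Adhesions at Week 6". On populations the section says "The Final Outcome assessment will be done for both the Safety and Per Protocol populations", and it names no denominator.

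Three other sections bear on this:

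- Section 4.6: "Analyses presented for the Per-Protocol (PP) will be considered primary".
- Section 4.6.1: Per-Protocol (PP) women need "an evaluable hysteroscopy at Baseline and Week 6 follow-up and completed the Week 6 follow-up visit". A reader-confirmed clean baseline is not required.
- Section 4.2.2: pre-existing adhesions exclude a woman "as determined by the investigator", so the readers play no part in eligibility.

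**The concern.** There are two linked faults.

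**The baseline check is one-sided.** Take a woman in whom the readers see a baseline adhesion that the investigator did not. If Week 6 is clean she joins the non-events; if it is not, she is Undetermined. The clean label is true for her, but under this rule she can never be a New Adhesion. Whether she is set aside depends on her Week 6 result. This can happen in PP as well as in Safety. In Safety, a woman without an evaluable baseline is treated the same way.

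**The display does not match the derivation.** Three outcomes are derived and two are shown. Undetermined women fit the words of the second displayed category, which would then mix new adhesions with adhesions the rule declines to call new. The text does not exclude two other treatments: keeping them only in the denominator, or dropping them. The no-imputation statement in section 4.6.9.2 does not settle it, because Undetermined is a derived category and not a missing value. Safety women with no Week 6 hysteroscopy receive no outcome at all.

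Newly formed adhesions are the only stated objective (section 3), and their incidence at six weeks is a primary variable (section 4.5.1.1). In a descriptive single-arm study this percentage is the main result, and two programmers could report it differently from the same data.

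**Working it through.** The SAP gives no adhesion rate, discordance rate or expected count, so there is no figure of its own to reproduce. The only input from the document is the maximum of 60 women (section 4.6.8). Everything else below is assumed.

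**Assumed quantities**, among women with an evaluable Week 6 hysteroscopy:
- p = risk of a new adhesion given a reader-clean baseline (the target)
- f = share with a reader-confirmed baseline adhesion (PP), plus those with no evaluable baseline (Safety)
- q = risk of Week 6 adhesions within that share

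**Expected percentage under each treatment of Undetermined:**
- Kept in the denominator only: p(1 − f). Shift from p: −pf.
- Dropped: p(1 − f)/(1 − fq). Shift: −pf(1 − q)/(1 − fq), which runs from −pf at q = 0 to 0 at q = 1.
- Counted as adhesions: p(1 − f) + fq. Shift: f(q − p), which runs from −pf at q = 0 to +f(1 − p) at q = 1.

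**With p = 10%:**

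| f | Treatment | q = 10% | q = 50% | q = 80% | q = 100% |
|---|---|---|---|---|---|
| 0 | all three | 10.0 | 10.0 | 10.0 | 10.0 |
| 5% | kept | 9.5 | 9.5 | 9.5 | 9.5 |
| 5% | dropped | 9.5 | 9.7 | 9.9 | 10.0 |
| 5% | counted | 10.0 | 12.0 | 13.5 | 14.5 |
| 10% | kept | 9.0 | 9.0 | 9.0 | 9.0 |
| 10% | dropped | 9.1 | 9.5 | 9.8 | 10.0 |
| 10% | counted | 10.0 | 14.0 | 17.0 | 19.0 |

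For example, at f = 5% and q = 50%: kept 0.10 × 0.95 = 9.5%; dropped 0.095/0.975 = 9.7%; counted 0.095 + 0.025 = 12.0%.

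The counted and kept figures differ by fq, the Undetermined women divided by N. At N = 60 that is 1/60 = 1.7 points per Undetermined woman.

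**In counts, with exact (Clopper-Pearson) 95% intervals.** Take 60 women, 6 reader-positive at baseline, with Week 6 adhesions in 3 of those 6 and in 5 of the other 54:
- Reader-clean baseline: 5/54 = 9.3% (3.1% to 20.3%)
- Kept: 5/60 = 8.3% (2.8% to 18.4%)
- Dropped: 5/57 = 8.8% (2.9% to 19.3%)
- Counted: (5 + 3)/60 = 13.3% (5.9% to 24.6%)

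**A smaller case.** One woman is reader-positive and has adhesions at Week 6, with 5 events among the other 59. The reader-clean and dropped figures are both 5/59 = 8.5%, kept is 5/60 = 8.3%, and counted is 6/60 = 10.0%.

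**No new adhesions.** With 0 New Adhesion and 3 Undetermined among 60, the counted figure is 3/60 = 5.0% although no adhesion was shown to be new.

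**The case against.** The strongest reply is that the one-sided check mislabels nobody: a cavity without adhesions at Week 6 has no new ones, whatever the baseline. A woman with a baseline adhesion could also form another, so removing her from the denominator is a choice of estimand. The rule gives Undetermined its own label, and section 4.6 summarizes categorical variables by counts and percentages, so the natural reading shows three levels over all PP women. Discordance would be visible, because section 4.6.4.1 also summarizes baseline ESH scores by investigator and by reader and presents reader agreement. The larger movements need the pooled reading and assumed rates. The study is exploratory, with no threshold.

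Much of this stands. The label is true, the rates are assumed, the PP effect is zero without discordance, and no decision rule is affected. Showing three levels over all PP women is a reasonable reading, but it is not what the opening sentence says, and it still gives the kept figure. The point about the risk set does not rescue the rule: whether or not such a woman could form a further adhesion, the rule never lets her be an event, so counting her only when she is a non-event pulls the percentage down. The planned baseline summaries are not cross-tabulated with Week 6, so a reader could not recover the incidence from them.

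**Conclusion.** The concern holds, and the section should be corrected. Relative to incidence among women with a reader-clean baseline, the reported New Adhesion percentage is too low, or at best equal, if Undetermined women are kept in the denominator or dropped. If they are counted under the second displayed category, it can err in either direction and no longer measures new adhesions.

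The one-sided check alone costs 1 point or less in the cases worked above. The larger movement comes from the unstated handling of Undetermined: 8.3% against 13.3% in the 60-woman example. These sizes show sensitivity and do not predict the result, because the frequency of discordance is unknown. The consequence is for how the main figure is read.

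**What to change.** Revise section 4.6.4.1 as follows.

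- Apply the readers' baseline check in both Week 6 branches.
- Numerator: no adhesion at baseline by the readers, and adhesion at Week 6.
- Denominator: no adhesion at baseline by the readers, and an evaluable Week 6 hysteroscopy.
- Show women with a reader-confirmed baseline adhesion (PP and Safety) and women with no evaluable baseline (Safety) in separate rows by Week 6 finding, outside the percentage.
- List Safety women without a Week 6 hysteroscopy as missing, in keeping with section 4.6.9.2.
- Align the opening sentence with these categories and state the denominator.
- As a sensitivity analysis, count Undetermined as new adhesions over all women with an evaluable Week 6 hysteroscopy.

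The cost is SAP wording and one derivation on data already collected. The denominator shrinks a little, so any interval reported would be slightly wider (3.1% to 20.3% for 5/54 against 2.8% to 18.4% for 5/60). The Safety percentage becomes nearly the same as the PP one, differing only through the visit-completion conditions in section 4.6.1. The separate rows and the missing count then carry the extra information from Safety.

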4.6.4.2 Other Efficacy Analysis

4.6.4.2.1 Overall Treatment Effect (OTE)

OTE will be summarized using descriptive statistics.

4.6.4.2.2 Subject Satisfaction

Subject Satisfaction will be summarized using descriptive statistics.

4.6.5 Procedure Summaries

The following procedure related information will be summarized using descriptive statistics:

- LOS (start of procedure to discharge)
- Time admission to discharge
- Procedure time (time of device insertion to removal)
- Patient Side (left, right, midline)
- Location (anterior, posterior, midline)
- Location (fundal, body, LUS, cornual, other)
- Fibroid type
- FIGO type
- Size of fibroids treated (visualized and ablated)
- Number of fibroids treated
- Number of fibroids per subject
- Number of ablations per fibroid
- Number of ablations per subject
- Number of ablated fibroids per subject

4.6.6 Transvaginal Ultrasound Summaries

The following transvaginal ultrasound related information will be summarized using descriptive statistics:

- Location (anterior, posterior, midline)
- Location (fundal, body, LUS, cornual, other)
- Patient Side (left, right, midline)
- Fibroid type
- FIGO type
- Maximum FIGO Type per subject
- Size of fibroids
- Number of fibroids
- Number of fibroids per subject

4.6.7 Safety Analyses

4.6.7.1 Adverse Events

Procedure safety will be assessed by recording all AEs that occur on the day of the treatment procedure. Longer-term safety will be assessed by recording at the follow-up visit any untoward medical occurrence since baseline. Each AE will be assessed for relationship to study device and/or procedure. In addition to evaluating procedural and longer-term safety, subjects who become pregnant after the procedure will be asked to report any pregnancy complications.

Descriptions of AEs will include the date of onset, the date the AE resolved, stabilized, or returned to baseline, and the outcome. All reported AEs will be summarized by the number of subjects reporting AEs, seriousness, and relationship to the Sonata System device and/or procedure. Summaries will also be presented for device-related AEs, and procedure-related AEs.

AEs will be summarized both by subject incidence rate and event incidence rate. In addition, AEs will be summarized by relationship to the Sonata System procedure and/or device, such that each subject will be counted only once for each AE by using the AE with the greatest relationship within each category. The sponsor is responsible for classifications of adverse events. Both investigator reported and sponsor evaluated classifications will be summarized.

4.6.7.2 EuroQOL EQ-5D

The EuroQOL EQ-5D will be summarized by visit using descriptive statistics.

4.6.7.3 Treatment Recovery Diary

The treatment recovery diary will be used to calculate the following parameters in days:

- Return to Normal Daily Activities
- Return to Normal Diet
- Return to Normal Sleep
- Return to Normal Urinary Function
- Return to Normal Bowel Movement

Each of these parameters will be summarized using descriptive statistics.

4.6.8 Determination of Sample Size

The sample size for this study is up to 60 subjects. This is an exploratory study and is not intended to be statistically powered.

